2. Resources Available to Conduct the Human Research:

(the aim here is to assess if the research is likely to be successful and thus justify the efforts and risks taken by the subjects):

Recruitment of patients will be through the practices of five orthopedic and/or neurological surgeons providing elective lumbar spinal fusion surgery. 12 physicians with specialized training in either spine surgery or regional anesthesiology with exquisite knowledge of the local study site, culture, and society and extensive research experience (numerous published studies) over the course of their careers entail the persons assisting with the trial. These individuals are all informed about the protocol, the investigational product(s), and their trial-related duties and functions. The study group will conduct weekly meetings via video or in-person conference to discuss the study protocol, investigational product(s), their trial-related duties and functions, and progress of the study in each stage.

3. Study Design:

a) Recruitment Methods (see PPHS policy):

Patients scheduled for a 1-2 level lumbar spinal fusion procedure will be identified at the time of the scheduled surgery. The study will be discussed and written consent will be provided for the patient to review and sign. A member of the research team will call the patient approximately 1 week prior to the surgery to discuss the study further and answer any questions the patient may have. This investigator will describe the study in detail, answer questions, confirm understanding, and review the consent form with the patient. Additionally, patients will be screened for inclusion and exclusion criteria in the clinic at the time of the scheduled procedure prior to the phone call 1 week before surgery. During the follow up phone call to answer any additional questions, the patient will be screened again for inclusion and exclusion criteria.

b) Inclusion and Exclusion Criteria:

Inclusion criteria: Adults aged greater than or equal to 18 years old and less than or equal to 85 years old. Patients who are scheduled to undergo lumbar spinal fusion surgery (1-2 level) and willing and able to provide informed consent.

	Protocol Name:	Erector Spinae Block for Spine Surgery
	Principal Investigator:	[name],
	Primary Contact Name/Contact Info:	[name] [contact]
	Date Revised:	11/15/2021
	Study Number:	Study 20-01312

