8. List any specialized grading system that will be used to evaluate adverse events (e.g., National Cancer Institute Common Toxicity Criteria).
N/A

9. Describe procedures that will be used to assure data accuracy and completeness.
All members are trained in proper data entry.

10. Should a temporary or permanent suspension of your study occur, in addition to the PPHS, indicate to whom (NIH, FDA, sponsor, IRB) will you report the occurrence.
IRB

 Mount Sinai	Protocol Name:	Erector Spinae Block for Spine Surgery
	Principal Investigator:	[name],
	Primary Contact Name/Contact Info:	[name] [contact]
	Date Revised:	11/15/2021
	Study Number:	Study 20-01312

i) Withdrawal of Subjects:

- Procedures for Subjects to Request Withdrawal:
 - (1) Patients are able to withdraw from the study at any point in the investigation. Patients will be provided with contact information and must withdraw in writing. If this decision is made prior to their procedure, the patient will undergo their procedure at the standard of care and not be included in the experimental protocol. If this decision is made following their procedure, the postoperative data collection will cease. The patient will receive standard postoperative care no matter the time of withdrawal from the study. All collected PHI will be destroyed at the time of withdrawal.
- Procedures for Investigator to Withdraw Subjects:
 - (1) If a patient must be withdrawn from the study by the investigators, the patient will be informed of such as soon as this decision is made. This may be due to changes in eligibility or if in the opinion of the investigator, they are not appropriate candidates for an Enhanced Recovery After Surgery protocol.
 - (2) If this decision is made prior to their procedure, the patient will undergo their procedure at the standard of care. If this decision is made following their procedure, the postoperative data collection will cease. The patient will receive standard postoperative care no matter the time of withdrawal from the study. All collected PHI will be destroyed at the time of withdrawal.

4. Provisions for Research Related Harm/Injury:

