	Study Number:	Study 20-01312

Participants will give verbal consent via telephone approximately 1 week prior to surgery. The patient will be seen preoperatively on the day of surgery to discuss the consent and answer any additional questions. At this time, the patient will sign written consent.

Children and cognitively impaired individuals are not included in the study.

Non-English speaking patients will be excluded secondary to unavailability of translated consent forms for all possible languages.

Where and When Consent Will Be Obtained:

Patients will be consented at the Icahn School of Medicine at Mount Sinai, first in the spine surgeon's office by [name] on [name], then in the pre-operative holding area by an anesthesiologist involved in this study, either [name], [name], [name], or [name], on the 3rd floor of the Guggenheim pavilion building on [name].

Waiting Period for Obtaining Consent:

Patients will have adequate time to decide to participate in the study. Patients are free to decline participation or discontinue participation at any time

10. Process to Document Consent in Writing:

The consent will be signed as described above. The patient will be given a copy of the consent form at signing. During the consenting process the consenter will review the consent form section by section with the patient.

11. Vulnerable Populations:

a) Unless already detailed in the protocol, please indicate which of the following populations are either included or excluded in this project: Indicate specifically whether you will include (target) or exclude each of the following populations:

Include	Exclude	Vulnerable Population Type

 
Mount Sinai
	Protocol Name:	Erector Spinae Block for Spine Surgery
	Principal Investigator:	[name],
	Primary Contact Name/Contact Info:	[name] [contact]
	Date Revised:	11/15/2021
	Study Number:	Study 20-01312

	x	Adults unable to consent
	x	Individuals who are not yet adults (e.g. infants, children, teenagers)
	x	Wards of the State (e.g. foster children)
	x	Pregnant women
	x	Prisoners

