- *If the Human Research involves pregnant women, review the “[CHECKLIST HRP-412 Criteria for Research Involving Pregnant Women](#)” to ensure that your protocol has sufficiently addressed these additional regulatory criteria for approval, including protocol specific information to support the determinations.*
- *If the Human Research involves non-viable neonates or neonates of uncertain viability, review the “[CHECKLIST HRP-413 Criteria for Research Involving Non-Viable Neonates](#)” “[CHECKLIST HRP-414 Criteria for Research Involving Neonates of Uncertain Viability](#)” to ensure that your protocol has sufficiently addressed these additional regulatory criteria for approval, including protocol specific information to support the determinations.*
- *If the Human Research involves Prisoners, review the “[CHECKLIST HRP-415 Research Involving Prisoners](#)” to ensure that your protocol has sufficiently addressed these additional regulatory criteria for approval, including protocol specific information to support the determinations.*

12. Multi-Site Human Research:

N/A

13. Community-Based Participatory Research

N/A

	Protocol Name:	Erector Spinae Block for Spine Surgery
	Principal Investigator:	[name],
	Primary Contact Name/Contact Info:	[name] [contact]
	Date Revised:	11/15/2021
	Study Number:	Study 20-01312

14. Sharing of individual and study Results with Subjects:

All results of the study will be shared with subjects if they wish to be notified through their preferred method of contact.

15. External IRB Review History

N/A

16. Control of Drugs, Biologics, or Devices:

Liposomal bupivacaine and 0.25% bupivacaine will be stored, handled, and controlled by the Mount Sinai Hospital Department of Anesthesiology, Perioperative and Pain Medicine in the departments medication refrigerator so that it will only be used on subjects and used only by authorized investigators. Plaine 0.25% Bupivacaine will be obtained by anesthesiologists deemed to be authorized investigators from the preoperative holding area prior to use on each patient in Groups 1 and 2 for the ESP block. Standard drug handling policies will be utilized for this study. All personnel handling medications are trained in this manner.

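### Section 3.i ties investigator withdrawal to the procedure and not to allocation or blinding, so opinion-based exclusion after the group is known is not ruled out

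*Protocol*

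**What the plan says.** Protocol Section 3.i, under the procedures for investigators to withdraw subjects, gives two grounds in item (1). The first is eligibility: "This may be due to changes in eligibility". The second is a judgement: "if in the opinion of the investigator, they are not appropriate candidates for an Enhanced Recovery After Surgery protocol". Suitability for such a pathway is not among the inclusion and exclusion criteria in 3.b.

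Item (2) splits the consequences by the timing of the procedure. Before it: "If this decision is made prior to their procedure, the patient will undergo their procedure at the standard of care". After it: "If this decision is made following their procedure, the postoperative data collection will cease". In both cases the protected health information already gathered is to be destroyed on withdrawal. Neither item mentions allocation, the group, or whether the person deciding is blinded.

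Three other places bear on the point:

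- **Section 3.a** puts the last stated eligibility screen at the telephone call about a week before surgery: "During the follow up phone call to answer any additional questions, the patient will be screened again for inclusion and exclusion criteria".
- **Section 9** has consent taken first in the surgeon's office and "then in the pre-operative holding area by an anesthesiologist involved in this study", with the written form signed on the day of surgery.
- **Section 16** says that plain 0.25% bupivacaine is "obtained by anesthesiologists deemed to be authorized investigators from the preoperative holding area prior to use on each patient in Groups 1 and 2".

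**The concern.** Randomised groups are comparable because nothing that happens after allocation decides who belongs to them. A rule that lets investigators remove patients on a subjective ground, with no cut-off at allocation, leaves that protection to conduct. If a patient who looks likely to do badly is removed more readily from one group than from the other, the remaining patients differ for reasons unrelated to the block.

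The loss could not be repaired later. An analysis plan can define who is analysed, but it cannot bring back data that were destroyed or never collected, and 3.i makes no provision for keeping a coded record of a withdrawn patient.

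**Working it through.** The plan states no figure on this point, so there is nothing to reproduce. The check has two parts: what the text establishes, and how large the effect could be.

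**What the text establishes**

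1. *Discretion.* Item (1) of 3.i rests partly on the investigator's opinion about something that 3.b does not list. No objective criterion is attached.
2. *Timing.* The only dividing line in item (2) is the procedure. Any moment up to surgery falls in the same branch, whether or not the group is known by then.
3. *Knowledge of the group.* Section 16 has authorised anesthesiologist-investigators obtain plain bupivacaine by patient before the block. Section 9 has study anesthesiologists take consent in the same holding area. In 3.h the principal investigator is described as someone who performs these interventions and is also the principal monitor. Blinding is mentioned only for the data items at the halfway safety review (3.h, item 5). Together these make it plausible that some investigators know the group before surgery. None of them states it.
4. *Late eligibility changes.* The last screen described is about one week before surgery, and the day-of-surgery contact in Section 9 is described only as a consent contact. A change arising in that week is handled by 3.i, which does not require the decision to come before the group is known.
5. *Follow-up.* The end of data collection is written only for the post-procedure branch. For the pre-procedure branch it is implied by withdrawal from the study and by the destruction of identifiable data.

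**How large it could be (illustration)**

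Inputs:

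- Total accrual is 84 (Section 3.c).
- Two equal groups are assumed, so 84 / 2 = 42 each.
- Removal of a fraction f = 0.10 of one group and none of the other is assumed. That is 0.10 × 42 = 4.2, or about 4 patients.
- The correlation ρ between the basis for removal and the outcome is assumed to be 0.5, with 1.0 as the upper bound.
- There is no true difference between groups, and the outcome is normal in SD units.

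Shift in the mean of the depleted group = ρ × φ(z at 1 − f) / (1 − f):

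- ρ = 1.0: φ(1.2816) / 0.90 = 0.1755 / 0.90 = 0.195 SD
- ρ = 0.5: 0.5 × 0.195 = 0.098 SD

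Standard error of the group difference = √(2/42) = 0.218 SD. The ratios are 0.195 / 0.218 = 0.89 and 0.098 / 0.218 = 0.45 standard errors.

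The table uses whole numbers removed from a group of 42 (f = k/42, SE = √(1/42 + 1/(42 − k))) and gives the two-sided type I error at nominal 5% from the normal approximation:

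| Removed from one group | Shift, ρ = 0.5 | Type I error | Shift, ρ = 1.0 | Type I error |
|---|---|---|---|---|
| 1 | 0.029 SD | 0.052 | 0.057 SD | 0.058 |
| 2 | 0.052 SD | 0.056 | 0.104 SD | 0.076 |
| 4 | 0.094 SD | 0.070 | 0.187 SD | 0.133 |

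Simulated t-tests (20,000 runs) for four removals gave 0.071 at ρ = 0.5 and 0.148 at ρ = 1.0.

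If there were three equal groups (84 / 3 = 28 each), four removals would give shifts of 0.132 SD and 0.263 SD, with type I errors of 0.076 and 0.157.

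**The case against.** The strongest objection is that a harmful window is assumed and not documented. A reader might infer that investigators know the group in the holding area and can then remove patients before surgery. The text does not support that as a fact. It does not say when allocation takes place, who learns the result, or who decides on withdrawal. The text available for review starts at Section 2 and does not describe the arms, so these points may be settled in the part not shown. If every such decision precedes allocation, exclusion cannot depend on the group.

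The drug-handling sentence is also weaker evidence than it looks. Plain bupivacaine is drawn for Groups 1 and 2 alike. If these are the only two groups, as the reference in 3.h to two treatments suggests, collecting it does not tell them apart. Section 16 places liposomal bupivacaine in the department's refrigerator for authorised investigators, but does not say when it is prepared or whether the preparer is blinded.

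A reader might further infer that a patient given the block and then withdrawn before surgery drops out of the safety record. That needs the block to precede surgery and the withdrawal to fall between the two. Neither is shown, and 3.h does provide for monitoring adverse events and dropouts.

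Finally, neither ground for withdrawal mentions the assigned block. If allocation follows written consent on the day of surgery, the window is a matter of hours. Four removals from one group and none from the other is an assumed input, and the upper figure needs perfect foresight of the outcome.

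All of this stands as a limit on the claim. It does not answer the core: the rule as written confines withdrawal neither to the time before allocation nor to a blinded decision-maker, uses a ground outside 3.b, and has identifiable data destroyed whatever the timing.

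**Conclusion.** The point holds as a weakness in how the rule is written. Section 3.i permits discretionary removal after allocation, with loss of data; the documents do not show that this will happen or that it will differ by group.

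Under the assumed 42 per group and about 4 one-sided removals, the bias is about 0.10 SD at a correlation of 0.5 and 0.195 SD at most, roughly 0.4 to 0.9 standard errors. It would not shrink with a larger trial if the same fraction were removed. One or two removals would matter little unless the reason for removal predicted the outcome almost perfectly. These figures illustrate scale and do not predict what the trial will see. The change is worth making because it is cheap and the lost data could not be recovered.

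**What to change.** Amend 3.a and 3.i as follows:

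1. Repeat the 3.b checklist in the preoperative holding area when written consent is signed, and open the group assignment only once it is passed.
2. Limit investigator withdrawal from the study to the time before the group is opened, and key the rule to that event and not to the procedure.
3. After that, keep the patient in the assigned group with all scheduled data collected and retained, whether or not the block is given, unless the patient withdraws consent.

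Clinical decisions, including whether the block is given, stay with the treating physician; the change concerns study membership and data only. If the part of the protocol not shown already places allocation after a final eligibility check, item 1 is met and a clarifying sentence in 3.i covers the rest.

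The cost is a short amendment and one more pass through an existing checklist at a contact that already takes place. The downside is that a few patients who did not receive the assigned block remain in their groups, which slightly dilutes the contrast.

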EPIC computerized medical record charting will be used to record data about the subjects. Additionally, investigators will ask patients questions (for example, nausea in PACU on 11 point Likert scale).
- Description of data that will be collected including long-term follow-up:
Age, Gender, BMI, ASA status, duration of surgery, total opioid use in PACU, total opioid consumption in 24 and 72 hours, severity of pain on Likert scale (0-10) at 1, 6, 12, 24, and 72 hours as well as at 2 weeks, 6 weeks, and 12 weeks post surgery, time to breakthrough pain after surgery (first dose of pain medication requested after surgery is finished), incidence of vomiting in PACU, nausea in PACU (highest number reported on 11 point Likert scale), time to ambulation after surgery, time to flatus after surgery, time to first bowel movement after surgery, analgesia satisfaction score 3 days after discharge, length of stay in PACU, Quality of recovery vis QoR-15 survey at 3 days, 2 weeks, 6 weeks, and 12 weeks postoperatively.

	Protocol Name:	Erector Spinae Block for Spine Surgery
	Principal Investigator:	[name],
	Primary Contact Name/Contact Info:	[name] [contact]
	Date Revised:	11/15/2021
	Study Number:	Study 20-01312

- Description of health information that will be viewed, recorded, or generated:
Age, Gender, BMI, ASA status, duration of surgery, total opioid use in PACU, total opioid consumption in 24 and 72 hours, severity of pain on Likert scale (0-10) at 1, 6, 12, 24, and 72 hours as well as 2 weeks, 6 weeks, and 12 weeks postoperatively, time to breakthrough pain after surgery (dose of pain medication beyond standard patient controlled analgesia regimen), vomiting in PACU, nausea in PACU (highest number reported on 11 point Likert scale), time to ambulation after surgery, time to flatus after surgery, time to first bowel movement after surgery, length of stay in PACU; length of stay in hospital, patient reported satisfaction with anesthesia, Quality of recovery vis QoR-15 survey at 3 days, 2 weeks, 6 weeks, and 12 weeks postoperatively.
- How PHI will be protected from improper use or disclosure:

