Only researchers involved in data collection and analysis will have access to patient data. All data collected by the researchers will be labeled with a one-way hash ID. Only the study investigators will have access to the full data set which will allow for matching of the has ID to the original data source. All researchers who will access the data have completed the institutional HIPAA certification. Extracted data will be de-identified before being given to the statistician for analysis. Any intermediary data files containing extracted PHI will be stored on secured hospital servers and destroyed after data analysis is complete. All study data at Mount Sinai stored electronically will follow MSMC policies. All PHI that is not stored on a limited access Mount Sinai IT maintained network drive will be encrypted and password protected. Statistical analysis will be carried out by a statistician employed by the Department of Anesthesiology. When the de-identified data set is released for analysis, a one-way hash ID will be generated for each record. Only Mount Sinai study investigators with access to the full data set will be able to match the hash ID to the original source.
- When and how PHI will be destroyed:
PHI will be destroyed following publication of this study. Digital encrypted files on the Mount Sinai network will be deleted permanently.
- Description of PHI that will be shared:

	Protocol Name:	Erector Spinae Block for Spine Surgery
	Principal Investigator:	[name],
	Primary Contact Name/Contact Info:	[name] [contact]
	Date Revised:	11/15/2021
	Study Number:	Study 20-01312

Age, Sex, BMI, ASA status, surgical procedure, opioid use. All other subject demographics will not be shared when de-identified data is given to a statistician employed by the department of anesthesiology.

- Justification for sharing PHI:

Deidentified data will be given to a statistician employed by the department of anesthesiology in order to complete the study analysis.

- With whom directly PHI will be shared:

Deidentified data will be given to a statistician employed by the department of anesthesiology

- Location where data will be stored:

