Extracted data will be de-identified before being given to the statistician for analysis. Any intermediary data files containing extracted PHI will be stored on secured hospital servers and destroyed after data analysis is complete. All study data at Mount Sinai stored electronically will follow MSMC policies. All PHI that is not stored on a limited access Mount Sinai IT maintained network drive will be encrypted and password protected.

- Duration data will be stored:

Data will be stored for the duration of the study. Encrypted data will be deleted permanently from the Mount Sinai network following completion of the study.

- Steps that will be taken to secure the data during storage use and transmission:

Extracted data will be de-identified before being given to the statistician for analysis. Any intermediary data files containing extracted PHI will be stored on secured hospital servers and destroyed after data analysis is complete. All study data at Mount Sinai stored electronically will follow MSMC policies. All PHI that is not stored on a limited access Mount Sinai IT maintained network drive will be encrypted and password protected.

- Data analysis plan including any statistical procedures:

Data analysis will be completed by a biostatistician employed by the department of anesthesiology.

 Mount Sinai	Protocol Name:	Erector Spinae Block for Spine Surgery
	Principal Investigator:	[name],
	Primary Contact Name/Contact Info:	[name] [contact]
	Date Revised:	11/15/2021
	Study Number:	Study 20-01312

g) Data and Safety Monitoring Plan:

- **For projects with a Data Safety Monitoring Board/Data Safety Committee (DMSB/DMC): N/A**
- *If not included in the protocol, attach a description of the DMC/DSMB, including the number, names (if available) and area of professional expertise of the members. The responsibilities of the DSMB/DMC must be clear as well as their powers and their degree of independence. The DSMB charter must be provided to the PPHS before the study may begin. Reports of the DMC/DSMB must be made available to the local PI and the MSSM PPHS. The report need not contain specifics of the study or data, but there should be clear statement if the study can continue as is, or requires changes or termination.*

h) For other projects with greater than minimal risk a monitoring plan must be provided:

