1. *List the name(s) of the individual(s) at MSSM who will be responsible for data and safety monitoring of this study. For each individual, indicate their role, name, title, and department information. The Principal Investigator may be the only monitor of a study.*
2. *If the qualifications of an individual to serve as a monitor are not contained in the PPHS application, they must be added to the DSMP either as a narrative description or as a CV.*

MSSM Principal Monitor: Principal Investigator

Last Name: [name]

First Name: [name]

Academic Title: Associate Professor

Department: Anesthesiology

Mailing Address: [name]

[contact]

Fax:

E-mail: [contact]

 Mount Sinai	Protocol Name:	Erector Spinae Block for Spine Surgery
	Principal Investigator:	[name],
	Primary Contact Name/Contact Info:	[name] [contact]
	Date Revised:	11/15/2021
	Study Number:	Study 20-01312

3. Justify your choice of principal monitor in terms of the assessed risk to the research subject's health and wellbeing. In high risk studies when the principal monitor is independent of the study staff, indicate the individual's credentials, relationship to the PI, and the rationale for selection.

This protocol is a minimal risk protocol comparing two standard of care treatments. As such, no more than minimal monitoring is required. As an anesthesiologist who performs these interventions, the PI is more than capable for this task.

4. List the specific items that will be monitored for safety (e.g., adverse events, subject compliance with the protocol, drop outs, etc.).

We will monitor for adverse events as well as dropouts.

5. Indicate the frequency at which ACCUMULATED safety and data information (items listed in number 3 above and interim analysis of efficacy outcomes) will be reviewed by the monitor(s) or the Data Monitoring Committee (DMC). Although this information must be reviewed at least annually, the higher the study risks, the more frequently reviews must be scheduled.

We will review blinded data items at the halfway point of the study to look for any safety issues. We will not be doing formal data analysis at that timepoint.

6. Where applicable, describe rules which will guide interruption or alteration of the study design.
N/A

7. Where applicable, indicate dose selection procedures that will be used to minimize toxicity.
N/A

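### Section 3.i stops postoperative data collection when an investigator withdraws a treated patient, although the patient has not withdrawn consent

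*Protocol*

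**What the plan says.** Protocol section 3.i describes two separate routes. In the first, the patient withdraws, in writing. In the second, the investigator withdraws the patient, either because eligibility has changed or because "in the opinion of the investigator, they are not appropriate candidates for an Enhanced Recovery After Surgery protocol". Item (2) of the investigator route provides for a decision made after surgery and repeats the consequence of the patient route: "If this decision is made following their procedure, the postoperative data collection will cease". Both routes end with "All collected PHI will be destroyed at the time of withdrawal".

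Other sections bear on this:

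- Section 3.b lists the entry criteria. Suitability for enhanced recovery is not among them.
- Section 3.f plans pain scores at 1, 6, 12, 24 and 72 hours and at 2, 6 and 12 weeks, and "Quality of recovery vis QoR-15 survey at 3 days, 2 weeks, 6 weeks, and 12 weeks postoperatively".
- Section 3.h, item 4, on safety: "We will monitor for adverse events as well as dropouts".
- Section 3.f, on coding: "All data collected by the researchers will be labeled with a one-way hash ID". Under the heading on PHI to be shared, the same section lists "Age, Sex, BMI, ASA status, surgical procedure, opioid use".
- Section 3.f, on storage: "Encrypted data will be deleted permanently from the Mount Sinai network following completion of the study". Section 6 instead keeps the study data without a time limit.

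**The concern.** An investigator's decision to withdraw a patient is not a withdrawal of consent. When the patient still agrees to be followed, there is no consent-based reason to stop asking for pain and recovery scores or to stop recording adverse events. The rule nevertheless ends both.

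Eligibility is screened before surgery, in clinic and again by telephone. A decision taken afterwards can therefore reflect what happened during or after the operation, and one of its grounds is a matter of opinion outside the entry criteria. The missing outcomes may then be related to the outcome itself.

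This cannot be left to an analysis plan. Patient-reported scores that were never requested do not exist, and section 3.i makes no exception for the adverse events that section 3.h undertakes to monitor.

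A smaller point is that section 3.i does not say what PHI covers, so the fate of a withdrawn patient's coded data up to that day is not stated.

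**Working it through.** The plan gives no withdrawal rate and no figure on this point, so there is nothing to reproduce. The check has four steps.

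**1. What is lost per patient.** From section 3.f there are 8 pain scores and 4 QoR-15 surveys, 12 in all.

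| Withdrawn just after | Pain scores lost | QoR-15 lost | Total |
|---|---|---|---|
| 24 hours | 4 | 4 | 8 of 12 |
| day 3 | 3 | 3 | 6 of 12 |
| week 2 | 2 | 2 | 4 of 12 |

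**2. Precision.** Section 3.c plans 84 patients. If a fraction d is lost, standard errors grow by 1/√(1 − d). For assumed d of 5%, 10% and 20%, about 80, 76 and 67 patients remain, and standard errors rise by about 3%, 5% and 12%.

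**3. Bias if all withdrawals fall in one arm.** The visible text does not state the arm size. Section 3.h speaks of two treatments compared. Section 16 mentions Groups 1 and 2 as those receiving plain bupivacaine for the block, which leaves a third group possible. Both 84/2 = 42 and 84/3 = 28 are therefore shown. Assumptions: no true effect, a normal outcome with SD 1 and higher values worse, and withdrawal of the k patients in one arm with the highest value of a score that correlates ρ with the lost outcome. Then

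bias = −ρ × k/(n − k) × m,

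where m is the expected mean of the k highest of n standard normal values. For k = 4, m is 1.717 (n = 42) and 1.514 (n = 28):

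- n = 42: 4/38 × 1.717 = 0.181. Times 0.3 gives -0.05 SD, and times 0.5 gives -0.09 SD.
- n = 28: 4/24 × 1.514 = 0.252. Times 0.3 gives -0.08 SD, and times 0.5 gives -0.13 SD.

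Simulation of the same model with a two-sample t-test at 0.05 (60,000 replicates) gives the same biases and these rejection rates:

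| Lost from one arm | n = 42, ρ 0.3 to 0.5 | n = 28, ρ 0.3 to 0.5 |
|---|---|---|
| 1 | 5.2 to 5.5% | 5.3 to 5.4% |
| 4 | 5.9 to 7.3% | 6.0 to 7.6% |
| 6 | 6.4 to 9.0% | 6.8 to 10.0% |

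**4. Withdrawal related to outcome but not to arm.** Here the k worst-scoring patients are dropped from the pooled sample. With k = 4 or 6 and no true effect, the bias is 0.00 SD and the rejection rate about 5%. With an assumed true effect of 0.6 SD, the estimate is drawn towards zero by only 0.01 to 0.05 SD.

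**The case against.** The strongest reply is that the one-arm scenario is an extreme. Under no true effect, withdrawals that follow the postoperative course without regard to arm fall evenly and inflate nothing. Inflation needs decisions that differ by arm. The visible text does not settle who is blinded; section 3.h refers only to a review of blinded data items. Suitability for enhanced recovery may mostly be judged before surgery, so post-procedure cases may be few, and one case hardly moves the error rate. All of this stands, and it limits the size of the point.

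Several outcomes, such as PACU opioid use, PACU nausea and 24-hour opioid consumption, are complete within a day, so a later withdrawal does not stop their collection. That also stands. The visible text names no primary endpoint, so the effect on the primary comparison cannot be stated.

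On safety, section 4 provides monitoring through recovery, a telephone number and return to hospital if needed, and section 3.i keeps standard care in place. What is lost is the research record of adverse events, not the patient's route to care.

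A reader might infer from "All collected PHI will be destroyed at the time of withdrawal" that outcomes already recorded are erased as well, which would make the bias much larger. The documents do not establish this. Sections 3.f and 6 mostly treat PHI as separable from the coded data. The list that includes opioid use stands under a PHI heading but is described there as what remains when de-identified data go to the statistician. The conflict over how long data are kept is real, but it concerns archiving and cannot bias the comparison.

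**Conclusion.** The point holds as a rule that should be changed, with a modest and conditional effect. Section 3.i plainly ends follow-up of treated patients on an investigator's decision while consent stands, and nothing visible provides otherwise.

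The certain consequence, whenever the rule is used, is lost patient-reported outcomes and adverse-event records, and some loss of precision. Bias in the group difference under no true effect arises only if withdrawals relate to outcome and differ between arms. With 4 lost from one arm it would be about -0.05 to -0.13 SD, with a type I error of about 6 to 8%. These figures rest on an assumed count, an assumed correlation of 0.3 to 0.5 and arms of 42 or 28. They show what could happen and do not forecast it.

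The scope of PHI is a matter for clarification, not evidence that outcomes are destroyed.

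**What to change.** In item (2) of the investigator-withdrawal part of section 3.i, replace the stop in collection with wording such as: *scheduled outcome and adverse-event collection continues after an investigator's post-procedure decision, unless the patient withdraws consent*. The consent form is not visible here and must be aligned so that it covers this follow-up. Clinical care stays with the treating team.

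As a secondary clarification, state in section 3.i that the PHI destroyed at withdrawal means identifiers, and that coded data collected up to withdrawal are kept as consent allows. Reconcile this with the PHI list and storage text in section 3.f and the retention statement in section 6.

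The cost is an amendment to protocol and consent wording, and a few more follow-up contacts for patients who would otherwise have been dropped. No extra patients or procedures are needed.
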